Study Design

This study will be a prospective, single-site, randomized, open-label study with institutional review board (IRB) approval. The study will be conducted in the neonatal intensive care unit (NICU) at the University of Tennessee Medical Center.

Study Treatment

Infants who have failed monotherapy with morphine sulfate and have documented informed consent will be randomized to receive phenobarbital (20 mg/kg load, then 5 mg/kg/day divided q12h) or clonidine (6 mcg/kg/day divided q3h). The phenobarbital and clonidine suspensions are 4 mg/mL and 10 mcg/mL, respectively. Study agents will be titrated to achieve control of symptoms (previous 24-hour average FS less than or equal to 8). The phenobarbital dose will be adjusted to obtain a desired trough of 25 to 30 mcg/mL. Levels will be obtained on Day 6, then weekly thereafter. Infants with a trough less than 25 will receive an adjusted load of phenobarbital 1 mg/kg for every 1 mcg/mL increase from obtained level to achieve a desired level of 25 mcg/mL and a change in the maintenance dose using a ratio of desired to measured phenobarbital level. Clonidine will be escalated by 1.5 mcg/kg/day every 24 hours (maximum 12 mcg/kg/day) to achieve control of symptoms. Blood pressure (BP) is documented prior to each clonidine administration. If hypotension occurs while receiving clonidine, the current dose will be held. If more than 2 clonidine doses are held in the previous 24 hours the total daily dose will be decreased by 1.5 mcg/kg/day. After control of symptoms, morphine sulfate will be weaned by 0.02 mg (0.05 mL) every 24 hours as tolerated until off. Morphine sulfate will be weaned if symptoms are controlled, and no rescue doses are required in the previous 24 hours. A rescue dose of morphine sulfate 0.02 mg (0.05 mL) may be given every 3 hours for consecutive FS greater than or equal to 11 while morphine sulfate is being weaned and after discontinuation. Infants who experience return of symptoms and require more than 2 rescue doses in the preceding 24 hours after discontinuing morphine will be placed back on the 0.02 mg (0.05 mL) until symptoms are controlled. Once symptoms are again controlled, a second attempt to discontinue morphine sulfate will occur. After morphine sulfate has been discontinued for 24 hours and symptoms are still controlled, the study agent can be weaned. Clonidine will be weaned by 25% (based on the dose at time of morphine sulfate discontinuation) every 24 hours over 72 hours. Infants will be observed for return of symptoms and rebound hypertension for 48 hours prior to discharge. Blood pressure will be measured every shift for 48 hours after discontinuation of clonidine. Infants who experience rebound hypertension or fail to maintain control of symptoms after

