
discontinuation of clonidine will be placed back on the last effective dose until symptoms are controlled. Once symptoms are controlled, weaning will resume. Infants receiving phenobarbital will also be observed for 48 hours after the discontinuation of morphine sulfate prior to discharge. Phenobarbital will be weaned as an outpatient based on the standard taper used in the NICU for over 5 years (Table 1).

Table 1: Standard phenobarbital taper based on dose at discharge

Phenobarbital dose on day of discharge	Standardized phenobarbital taper initiated upon discharge
5.1 to 7 mg every 12 hours	6 mg two times a day for 1 week, then 4 mg two times a day for 1 week, then 2 mg two times a day for 1 week, then 2 mg once a day for 1 week, then stop
7.1 to 9 mg every 12 hours	8 mg two times a day for 1 week, then 6 mg two times a day for 1 week, then 4 mg two times a day for 1 week, then 2 mg two times a day for 1 week, then stop
9.1 to 11 mg every 12 hours	10 mg two times a day for 1 week, then 8 mg two times a day for 1 week, then 4 mg two times a day for 1 week, then 2 mg two times a day for 1 week, then stop
11.1 to 13 mg every 12 hours	12 mg two times a day for 1 week, then 8 mg two times a day for 1 week, then 6 mg two times a day for 1 week, then 2 mg two times a day for 1 week, then stop
13.1 to 15 mg every 12 hours	14 mg two times a day for 1 week, then 10 mg two times a day for 1 week, then 6 mg two times a day for 1 week, then 4 mg two times a day for 1 week, then stop

If symptoms are unable to be controlled with the study agent alone, the addition of the nonrandomized medication (phenobarbital/clonidine) may be initiated to control symptoms. Morphine, clonidine and phenobarbital, in that order, will be weaned per protocol.

The patient medical record will be reviewed to collect data about the subjects. This includes the patient’s electronic medical record and chart.

Risks to subjects

Risks to participants include side effects associated with study medication, potential increased length of stay/treatment compared to those patients receiving comparative medication and loss of confidentiality. Both of the study medications are commonly used in this patient population and considered standard of care with no evidence of superiority in the treatment of NAS.

Benefits to subjects

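### The schedule builds a gap of about 4 days into time to discharge, which Data Management still treats as the primary endpoint although Study Endpoints has moved to length of morphine therapy

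*Combined protocol and SAP*

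**What the plan says.** **Clonidine after morphine stops (Study Treatment).** The wean begins only after a wait: "After morphine sulfate has been discontinued for 24 hours and symptoms are still controlled, the study agent can be weaned". The wean itself is: "Clonidine will be weaned by 25% (based on the dose at time of morphine sulfate discontinuation) every 24 hours over 72 hours". Then: "Infants will be observed for return of symptoms and rebound hypertension for 48 hours prior to discharge". The next sentence ties a 48-hour period to the end of clonidine: "Blood pressure will be measured every shift for 48 hours after discontinuation of clonidine".

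**Phenobarbital after morphine stops (Study Treatment, continued).** "Infants receiving phenobarbital will also be observed for 48 hours after the discontinuation of morphine sulfate prior to discharge". The taper follows discharge: "Phenobarbital will be weaned as an outpatient based on the standard taper used in the NICU for over 5 years". Every row of Table 1 has four one-week steps.

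**Departures from the simple course (Study Treatment).** Infants whose symptoms return and who need more than two rescue doses in 24 hours after stopping morphine "will be placed back on the 0.02 mg (0.05 mL) until symptoms are controlled". In either arm, "the addition of the nonrandomized medication (phenobarbital/clonidine) may be initiated to control symptoms". An infant on all three drugs comes off morphine first, then clonidine, then phenobarbital.

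**Endpoints and analysis.** Study Endpoints, as revised, makes length of morphine therapy primary and moves time from adjunct start to discharge to the secondary list, beside length of stay. Data Management does not follow the revision. It names time to discharge as primary, lists morphine length as secondary, and states the 1.2-day detectable difference at 25 per arm for time to discharge. It also plans a 30-day readmission odds ratio without saying when the 30 days begin.

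**The concern.** Two sections of current text name different primary endpoints, and the two endpoints respond differently to the weaning schedule. Time to discharge contains an interval that the protocol itself makes longer with clonidine. Length of morphine therapy normally ends before either adjunct is weaned.

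If the analyst follows Data Management, the primary test is on the endpoint that carries the scheduled gap. With identical morphine duration in both arms, time to discharge would still be expected to differ by about that gap. A result reported without this explanation could be credited to the drug when it comes from where the wean takes place. The only detectable difference that the plan states at 25 per arm also belongs to time to discharge, so the revised primary endpoint has no power statement of its own.

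**Working it through.** **1. Scheduled time from morphine stop to discharge, one adjunct, no complications.** All inputs are from Study Treatment.

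| | Clonidine | Phenobarbital |
|---|---|---|
| Wait after morphine stop | 24 h | none added |
| Inpatient wean | 72 h | 0 h (tapered at home) |
| Observation before discharge | 48 h | 48 h, from morphine stop |
| Total | 24 + 72 + 48 = 144 h | 48 h |

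Gap = 144 − 48 = 96 h = 4 days: a 3-day wean plus a 1-day wait. The observation period is equal in length and cancels; only its starting point differs.

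**2. Effect of adding the other adjunct.** A phenobarbital-arm infant who adds clonidine is weaned from clonidine before phenobarbital, so I give that infant the 144 h path. A clonidine-arm infant who adds phenobarbital stays at 144 h. If a fraction q of the phenobarbital arm adds clonidine, the mean gap is 4 × (1 − q). The documents give no q, so these values are assumed:

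- q = 0: 4.0 days
- q = 20%: 4 × 0.8 = 3.2 days
- q = 40%: 4 × 0.6 = 2.4 days

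**3. The plan's own power figures.** The inputs are d = 3.0667, two-sided 5% and equal allocation. At 4 per arm the noncentrality is 3.0667 × √(4/2) = 4.337, the critical t is 2.447 on 6 df and the power is 0.9475, as the plan states.

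At 25 per arm, a t test has 80% power at d = 0.809. Under normality the Mann-Whitney test needs 0.809 / √(3/π) = 0.828 SD.

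- SD that the 1.2-day figure requires, if 80% power is meant: 1.2 / 0.809 = 1.48 days (t test), or 1.2 / 0.828 = 1.45 days (Mann-Whitney). Data Management states no SD.
- If the 5-day difference belongs with the printed d, the SD is 5 / 3.0667 = 1.63 days and the t-test detectable difference is 0.809 × 1.63 = 1.32 days.
- At assumed SDs for morphine length, the Mann-Whitney detectable difference is 0.828 × 4.5 = 3.7 days and 0.828 × 8 = 6.6 days.

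**4. Gap against the stated target.** 4 / 1.2 = 3.3. The ratio uses the plan's figure as printed, so it inherits the unstated SD of about 1.5 days.

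**5. Illustration.** The assumptions are normal data, equal morphine duration in both arms, a 4-day gap, q = 0 and 25 per arm. The simulated chance that a Mann-Whitney test on time to discharge is significant in favour of phenobarbital is 0.85 at SD 4.5, 0.39 at SD 8 and 0.14 at SD 15. These SDs are assumed. At the SD of 1.63 days implied by the power listing, significance is almost certain (about 1.00). None of these is a false-positive rate, because the arms do differ in time to discharge.

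**6. Readmission.** Each Table 1 taper lasts 4 × 7 = 28 days. If the window opens at discharge, an infant on phenobarbital alone is on the taper for 28 of 30 days, and an infant on clonidine alone for none.

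**The case against.** The strongest reply is that the revision has already dealt with the matter: Study Endpoints makes morphine length primary, and the gap stays out of it barring a restart. What is left at primary level is text in Data Management that was not updated. That is largely right, and it limits the concern. But the un-updated text is the analysis section, and it carries the test for the primary endpoint and the stated detectable difference. An analyst working from it would run a different trial.

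Four stronger readings are tempting, and the documents support none of them.

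- *A significant discharge difference would be spurious.* It would not. Home taper against inpatient wean is part of what is being compared, and earlier discharge is one of the benefits that Benefits to subjects hopes to learn about. Time to discharge is a valid comparison of whole strategies. Risks to subjects also discloses a possibly longer stay.
- *The plan intends discharge time to show symptom control.* No section says so. Benefits to subjects lists symptom control, side effects and earlier discharge as separate possibilities.
- *The gap could be 3 or 5 days.* Three days requires the wait to fall inside the 72 h, but weaning may start only after morphine has been off for 24 h. Five days extends the wean to 96 h, against the stated 72 h. Four 25% cuts at 0, 24, 48 and 72 h fit the text.
- *The readmission odds ratio is biased.* The direction of any effect is unknown, and being on a home taper belongs to the phenobarbital strategy. Discharge is the natural start of the window. What is missing is a definition and a note, not a different analysis.

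**Conclusion.** The concern holds in a limited form. The schedule puts about 4 days (144 h against 48 h) between the arms in time to discharge and length of stay. This assumes an uncomplicated course on a single adjunct. The average gap shrinks as more phenobarbital-arm infants add clonidine, and restarts can change it for an individual infant.

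Under Study Endpoints the gap touches secondary endpoints only. Under Data Management it sits in the primary analysis. The two sections cannot both stand, and the 1.2-day detectable difference is stated for the endpoint that the revision demoted. That figure also needs an SD of about 1.5 days if 80% power is meant. The 4-day gap is arithmetic on the protocol's schedule. The chance of a significant discharge result cannot be fixed from the documents, because it depends on an SD for time to discharge that they do not give. The readmission point is minor.

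**What to change.** These changes concern the analysis text only. Treatment, weaning and discharge rules are untouched.

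1. **Reconcile Data Management with Study Endpoints.** Name length of morphine therapy as primary, tested by Mann-Whitney, and time from adjunct start to discharge as secondary. Restate the detectable difference for morphine length together with the SD used: about 0.83 SD at 25 per arm and 80% power under normality.
2. **Report time to discharge and length of stay as Hodges-Lehmann differences with 95% confidence intervals.** Label them as comparisons of whole strategies that include a scheduled gap of about 4 days. Give the number in each arm who received both adjuncts beside them; the percentage on triple therapy is already a secondary endpoint.
3. **Minor: state that the 30-day readmission window starts at discharge.** Keep the planned odds ratio and note beside it that the phenobarbital taper covers 28 of those 30 days.

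No longer readmission window or further split by taper status is needed. With about 50 infants these would add follow-up and small counts for little information.

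The cost is wording and no new data collection. The detectable difference will look less favourable than 1.2 days unless the SD of morphine length is near 1.5 days.

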The primary endpoint of this study is the **length of morphine sulfate therapy** ~~time from initiation of adjunctive therapy until hospital discharge in the two groups~~. Secondary end points include **time from initiation of adjunctive therapy until hospital discharge in the two groups**, length of stay, ~~length of morphine sulfate therapy~~, percentage of patients requiring triple therapy, safety and readmission rates.

Number of subjects

Approximately 50 patients will be enrolled in the study.

Inclusion / Exclusion Criteria

Inclusion Criteria

Infants greater than or equal to 35 weeks admitted to the neonatal intensive care unit (NICU) who have failed monotherapy with morphine sulfate will be eligible for enrollment in the study. Infants considered to have failed morphine sulfate therapy are those whose dose exceeds 0.15 mg (0.4 mL) q3h or have failed two attempts at weaning after initial stabilization.

Exclusion Criteria

Infants who develop NAS due to iatrogenic causes (analgesia or sedation), are unable to take oral medications at any point during their treatment or are in the custody of the department of child protective services with no legal guardian identified at the time of enrollment will be excluded.

Recruitment Methods

Subjects will be identified through medical record screening, contact with investigators patients in the clinical setting and referral from non-investigators (physicians, nurse practitioners or physician assistants).

Consent process

- An informed consent will be obtained from the parent or legal guardian for all infants enrolled in the study.
- A notice of research will be provided with the admission documents to the parent/legal guardian of all infants being admitted for NAS. If the patient fails monotherapy, the informed consent interview will be conducted and consent obtained over the phone. The full signed consent will be left at the patient bedside and given to the parent/legal guardian at their next visit to the hospital.

- The informed consent interview will be conducted over the phone by study personnel if the legal guardian is not present at the time it is determined that an adjunctive agent is needed to control the study participants' symptoms of NAS. Documentation of consent by the legal guardian will be noted by the study investigator and a witness. A copy of the informed consent will be left at the subject bedside to be provided to the legal guardian at the next visit to the NICU.

Methodology

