It is not known if one of the study medications will better control withdrawal symptoms, allow us to wean oral morphine faster, have fewer side effects or allow the infant to be

discharged from the hospital sooner. The knowledge gained from this research will help us determine if clonidine or phenobarbital could better control symptoms of withdrawal, have less side effects or allow children to be discharged from the hospital sooner.

Data Management

- The primary endpoint of time from initiation of adjunctive therapy until hospital discharge will be assessed using Mann-Whitney U test. Secondary Endpoints of length of stay and length of morphine therapy will also be assessed via Mann-Whitney U test. Side effects and readmission rate via chi-squared with an unadjusted odds ratio with 95% CI for 30-day readmission.
- A power analysis was completed for sample size (based on Surran et al findings with power to detect a 5-day difference in treatment time):

t tests – Means: Difference between two independent means (two groups)		
Analysis:	A priori: Compute required sample size	
Input:	Tail(s)	= Two
	Effect size d	= 3.0666667
	α err prob	= 0.05
	Power (1- β err prob)	= 0.80
	Allocation ratio N2/N1	= 1
Output:	Noncentrality parameter δ	= 4.3369216
	Critical t	= 2.4469119
	Df	= 6
	Sample size group 1	= 4
	Sample size group 2	= 4
	Total sample size	= 8
	Actual power	= 0.9475121

It is predicted that a sample size of 25 in each treatment group will be powered to detect 1.2-day difference in time from initiation of adjunctive therapy until hospital discharge.

- All paper research records containing data from individual subjects will be locked and stored. All electronic research records containing data from individual subjects will be computer password protected. All records will be accessible only to research personnel.

Withdrawal of Subjects

Subjects may withdraw their permission for participation in research at any time. Subjects will contact [name] in writing to let us know they are withdrawing their permission. □ The mailing address is [name]. □ At that time, we will stop further collection of any information. □ However, the health information collected before this withdrawal may continue to be used for the purposes of reporting and research quality.

References

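### Symptom control is a stated question, but the plan assesses it only indirectly: no endpoint uses the protocol's own definition of control

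*Combined protocol and SAP*

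**What the plan says.** - **Benefits to subjects** names four unknowns: which drug better controls withdrawal, allows faster morphine weaning, has fewer side effects, or allows earlier discharge. It then says the knowledge gained will help to "determine if clonidine or phenobarbital could better control symptoms of withdrawal, have less side effects or allow children to be discharged from the hospital sooner".
- **Study Endpoints** makes "length of morphine sulfate therapy" the primary. The secondaries are time from adjunct start to discharge, "length of stay", and "percentage of patients requiring triple therapy, safety and readmission rates".
- **Study Treatment** defines control: "Study agents will be titrated to achieve control of symptoms (previous 24-hour average FS less than or equal to 8". It then ties weaning to control: "After control of symptoms, morphine sulfate will be weaned by 0.02 mg (0.05 mL) every 24 hours as tolerated until off". Each step also requires that no rescue dose was needed in the preceding 24 hours.
- **Study Treatment, after Table 1**, gives the trigger for triple therapy: "If symptoms are unable to be controlled with the study agent alone, the addition of the nonrandomized medication (phenobarbital/clonidine) may be initiated".
- **Data Management** states: "The primary endpoint of time from initiation of adjunctive therapy until hospital discharge will be assessed using Mann-Whitney U test". It applies the same test to length of stay and morphine duration, and chi-squared to side effects and readmission. It names no test for triple therapy and no analysis of FS, time to control or rescue doses.

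**The concern.** The protocol treats control and faster weaning as separate questions, so morphine duration cannot simply be taken as the measure of control. Weaning, side effects and discharge each have a matching endpoint; control has no direct one, although it is defined and assessed daily to run treatment.

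Speed of control is also where the two regimens differ by design. Phenobarbital begins with a load. Clonidine begins at 6 mcg/kg/day and rises by 1.5 every 24 hours to at most 12, so up to (12 − 6)/1.5 = 4 daily escalations. If the plan is followed as written, the report can say which arm came off morphine or went home sooner. It cannot say directly which arm reached control sooner or held it better.

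**Working it through.** The plan gives no figure for control. Its one calculation, the sample size, reproduces: 3.0666667 × √(4/2) = 4.3369 with 6 degrees of freedom, and power 0.9475 at 4 per arm. It does not bear on this point.

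**Step 1. Match each stated question to an endpoint.**

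| Question in Benefits | Matching endpoint |
|---|---|
| Better control of symptoms | None direct |
| Faster morphine weaning | Morphine duration |
| Fewer side effects | Safety |
| Earlier discharge | Time from adjunct start to discharge; length of stay |

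**Step 2. Ask what the indirect measures carry.**

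*Triple therapy* is a control-failure outcome by its trigger. It is yes/no, has no score threshold or time limit, is started at discretion in an open-label trial, and says nothing about speed.

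*Morphine duration* can be written as T = P + C + W + M + R:
- P: morphine before the adjunct. The start of the clock is not defined, so P may or may not count.
- C: time from adjunct start to control.
- W: minimum number of daily wean steps, the starting dose divided by 0.02 mg and rounded up.
- M: days on which a step was missed.
- R: any return to morphine after stopping.

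The drugs can act on C, M and R. T is their sum together with P and W, so it reflects control but cannot separate speed of control from the rest.

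*Time to discharge and length of stay* also include the schedule after morphine, which differs by arm. Reading the 48-hour observation as following the end of clonidine, that schedule is 24 + 72 + 48 = 144 h for clonidine against 48 h for phenobarbital. The gap is 96 h, or 4 days. These outcomes are therefore weaker stand-ins for control than morphine duration.

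**Step 3. Ask whether the shared wean distorts the primary.** From just above 0.15 mg, 0.15/0.02 = 7.5, so W is at least 8 steps; from 0.20 mg it is 10. A constant added to every infant cannot change ranks. In a generated example with 25 per arm, the Mann-Whitney p-value was 0.0775 both with and without 8 days added. Only spread in W between infants costs power. An illustrative simulation assumed 25 per arm, a 2.5-day difference and SD 3 days. Power was 0.79, 0.69, 0.50 and 0.29 when W had SD 0, 1.5, 3 and 5 days. The documents do not give the spread of W.

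**The case against.** Control is not ignored. Triple therapy records failure of control by arm. Morphine duration depends on control throughout: weaning starts only after control, every step requires it, and loss of control after stopping can return the infant to morphine. The quoted aim is Benefits text, not the Objective, and promises only to help determine the answer. Time to control would compare regimens with different built-in speeds, scored open-label. All of this stands. It makes the measurement indirect rather than absent, and any new outcome supportive only.

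A reader might go further and infer three things that the documents do not support.

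- *That no endpoint reflects control.* Triple therapy and morphine duration both do.
- *That the primary is dominated by a fixed wean.* The step size is common to both arms, but steps are taken only as tolerated. With 8 to 10 steps and control in an assumed 1 to 4 days, the wean would be 8/(8 + 4) = 67% to 10/(10 + 1) = 91% of morphine time after adjunct start. That also assumes no missed step, which is doubtful when infants can enter because two weaning attempts failed. With 4 missed days the same scenarios give 8/16 = 50% to 10/15 = 67%. For assumed totals of 10, 15, 20 and 30 days, 8 steps are 80%, 53%, 40% and 27%. No expected duration is stated, and neither is the entry dose for infants admitted after failed weans, so no share can be established.
- *That a shared minimum hides a real difference.* If control comes a day sooner and nothing else changes, morphine ends a day sooner. Variation in starting dose could dilute the comparison, but its size is unknown.

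**Conclusion.** The point holds in a limited form. Control is a stated question with a protocol definition, yet it is assessed only through a discretionary treatment decision and through durations that mix it with other components. This is a low-cost improvement and not a threat to the validity of the primary comparison. The conclusion rests on setting the sections side by side and needs no numerical assumption. The power of a time-to-control comparison with about 25 infants per arm cannot be stated, because the documents give no distribution for it.

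Separately, Study Endpoints makes morphine duration primary while Data Management still names time from adjunct start to discharge. That conflict needs resolving whether or not a control endpoint is added.

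**What to change.** 1. In Study Endpoints, add a named secondary: time from first adjunct dose to the first 24 hours, falling wholly after that dose, with average FS at or below 8.
2. In Data Management, compare it by randomised arm with the Mann-Whitney test already planned. Give infants who receive the non-randomised drug before control the worst rank, tied. The test uses order only, so no time need be invented for them. State in advance how an infant who leaves the study before either event is handled.
3. Add a supporting secondary: number of days on which a morphine wean step was not taken because the control or rescue condition was not met.
4. If these are not added, narrow the Benefits wording to the outcomes actually measured.
5. Make Study Endpoints and Data Management name the same primary endpoint.

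The cost is wording and modest extra chart abstraction of scores and rescue doses already used for daily decisions; treatment does not change. Because FS is scored open-label, both additions should be labelled supportive.

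### Two current sections name different primary endpoints, and the 25-per-group power statement belongs to the one that Study Endpoints demotes

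*Combined protocol and SAP*

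**What the plan says.** The combined protocol and SAP, dated June 2018 and revised March 2020, shows tracked markup in Study Endpoints. The resulting text reads "The primary endpoint of this study is the length of morphine sulfate therapy". Time from adjunct start to discharge is struck out as primary and reinserted lower down: "Secondary end points include time from initiation of adjunctive therapy until hospital discharge in the two groups".

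Data Management shows no markup. Its first bullet says "The primary endpoint of time from initiation of adjunctive therapy until hospital discharge will be assessed using Mann-Whitney U test", followed by "Secondary Endpoints of length of stay and length of morphine therapy will also be assessed via Mann-Whitney U test".

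The sample-size text, also in Data Management, has two parts. The power printout is introduced as based on a cited trial, "with power to detect a 5-day difference in treatment time". The closing sentence says that 25 per group is "powered to detect 1.2-day difference in time from initiation of adjunctive therapy until hospital discharge".

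Study Treatment sets what happens after morphine stops. For both arms, "After morphine sulfate has been discontinued for 24 hours and symptoms are still controlled, the study agent can be weaned". In hospital, "Clonidine will be weaned by 25% (based on the dose at time of morphine sulfate discontinuation) every 24 hours over 72 hours". There is a 48-hour pre-discharge observation for return of symptoms and rebound hypertension, and blood pressure is checked for 48 hours after clonidine ends. Phenobarbital infants are observed for 48 hours after morphine ends and taper the drug as outpatients.

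**The concern.** The two sections assign the primary and secondary labels in opposite ways to the same two outcomes. Mann-Whitney U is named for both, so the test itself is settled. What is open is which result is confirmatory and which outcome the 25 per group was chosen for.

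In an open-label trial this leaves room for the choice to follow the data. An analyst working from Data Management would report discharge as primary, and one working from Study Endpoints would report morphine length. Each could cite current text. The plan gives no testing order or multiplicity rule.

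The two outcomes also measure different things. Time to discharge includes the in-hospital clonidine wean and the observation after it, which have no inpatient counterpart on phenobarbital. Morphine length includes neither. The trial could therefore reach different, even opposite, conclusions depending on which section is followed.

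**Working it through.** **1. The plan's own printout.** Inputs from Data Management: two-sided alpha 0.05, d = 3.0666667, 1:1 allocation, target power 0.80. With n = 4 per group, df = 6 and the noncentrality is d × √(n/2) = 3.0667 × √2 = 4.337. The critical t is 2.447 and the power 0.9475. This reproduces the printed figures. Three per group gives 0.799, just short of 0.80. The printout is internally correct, but its outcome is labelled only as treatment time.

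**2. The 25-per-group sentence.** It names time to discharge and gives no SD. For a two-sample t-test at two-sided 0.05 and 80% power, 25 per group detects d = 0.809. The stated 1.2 days therefore implies SD = 1.2 / 0.809 = 1.48 days. The printout implies SD = 5 / 3.0667 = 1.63 days, at which 25 per group has 72% power for 1.2 days. No statement expressed in days at 25 per group exists for morphine length.

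**3. Detectable difference if morphine length is primary.** By t-test it is 0.809 × SD. For Mann-Whitney with normal data (efficiency 3/π = 0.955) it is 0.809 / √0.955 = 0.828 × SD. The documents give no SD, so these are assumptions:

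| Assumed SD (days) | t-test (days) | Mann-Whitney (days) |
|---|---|---|
| 3 | 2.43 | 2.48 |
| 7 | 5.66 | 5.80 |

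**4. Scheduled stay after morphine stops (Study Treatment).**
- Clonidine: 24 h off morphine + 72 h wean + 48 h observation = 144 h. If the observation overlapped the wean: 24 + 72 = 96 h.
- Phenobarbital: 48 h.
- Gap: 144 − 48 = 96 h (4 days), or 96 − 48 = 48 h (2 days) with overlap.

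Either gap exceeds the 1.2 days the plan says it can detect.

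**5. Effect on the discharge test.** Illustration: equal morphine days in both arms, all stays at the scheduled minimum, normal data, 25 per group, Mann-Whitney U at two-sided 0.05, simulated. Share of trials in which the discharge test favours phenobarbital:

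| Assumed SD (days) | 2-day gap | 4-day gap |
|---|---|---|
| 3 | about 61% | about 99% |
| 7 | about 15% | about 48% |

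At the SDs of 1.48 to 1.63 implied by the plan's own figures, the share is 98% to 100%. With no gap, as for morphine length here, each arm is favoured in about 2.5%.

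**6. If either outcome could be claimed as primary.** Testing both at 5% gives a chance of at least one false positive of 1 − 0.95² = 9.75% if they are independent, about 9.1% at an assumed correlation of 0.5 and 7.8% at 0.8.

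**The case against.** The best counter-argument is that the sponsor's intent is visible. The markup is a deliberate two-way swap in a dated revision, the only visible edit runs towards morphine length, and both outcomes keep the same test. On that reading this is a missed conforming edit. The intent is indeed clear enough to draft the correction. But the analysis and sample-size text is equally current and directs the analyst to the other outcome, so the conflict is real until it is corrected.

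The printout may also already concern morphine days: the cited trial's title in the reference list refers to reducing days of morphine therapy. That is plausible, but the plan does not say it, and the sentence that justifies 25 per group plainly names discharge.

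The numbers can be challenged too. SDs of 3 and 7 have no source in the documents. The 2-day gap rests on the less natural reading, because blood pressure checks run for 48 hours after clonidine has stopped. Both points are fair. The SDs are only a range, and the 2-day gap is a cautious lower bound. The natural reading and the plan's implied SDs both make the effect larger.

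Finally, the undefined start and stop of morphine therapy is a separate gap that would remain if the sections agreed. It does not support the severity here, but should be closed in the same edit.

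**Conclusion.** The concern holds and must be fixed before analysis. Two current sections contradict each other on the primary endpoint, and the 25-per-group sentence is written for the outcome that Study Endpoints makes secondary. This rests on the text alone and needs no assumption.

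The consequence is material because the schedule itself lengthens the clonidine stay by 2 to 4 days. How often that alone would turn the discharge test towards phenobarbital depends on an SD the documents do not give. Restarts of morphine and use of the second adjunct will also move actual stays away from the schedule, so opposite conclusions are possible, not certain.

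**What to change.** Have the sponsor confirm the primary endpoint, and rewrite the first bullet of Data Management to match Study Endpoints. Suggested text: *The single primary endpoint is length of morphine sulfate therapy, compared between groups by Mann-Whitney U test at two-sided 0.05. Time from adjunct start to discharge and length of stay are secondary.*

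In the same edit:
- Define the morphine interval: whether it starts at the first morphine dose or at adjunct start, that it ends at the last dose, and how restart days and rescue doses count. Study Treatment allows both after discontinuation.
- Replace the 1.2-day sentence with the detectable difference for morphine length at 25 per group, using an SD with a stated source.
- Report time to discharge as the originally planned primary, and state when and why the primary was changed and whether outcome data had been seen by then. The revision is dated about 20 months after the original, and the study is open-label.

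The cost is protocol wording and one sourced SD. The wording needs no extra patients. The restated detectable difference may be less favourable than 1.2 days. Purely as an example, at an assumed SD of 7 days, 25 per group gives about 70% power for 5 days by t-test, and 80% would need 32 per group.
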